### 3. **Research Design and Methods**

This case series will assess the efficacy for alveolar ridge expansion and change in peri-implant density when prepared by the osseodensification technique. The retention of this volume throughout osseointegration and loading will be evaluated. The changes in bone volume will be recorded by CBCT and intra-surgical direct measurements. A standardizing stent will be used to for direct measurements with a caliper. Radiopaque markers on this stent will guide the measurements on the CBCT. CBCT will be taken before and after osseodensification, and 1 year after delivery of final restoration. Standardized ~~periapical and~~ **bitewing** radiographs will be taken as well to evaluate marginal bone loss and peri-implant bone density. Calibrated examiners will evaluate implant survival and failure rate, ISQ value,

peri-implant pocket depth, plaque index, bleeding index, gingival index, biological and restorative complications.

All the surgical interventions and follow-up appointments will be conducted at the University of Oklahoma, Graduate Periodontics clinic. Restorative interventions will be scheduled with the restorative dentist of the patient's choosing. Approximately 10 visits are anticipated for each patient. Additional appointments may be needed depending on surgical or restorative complications that need attention or intervention. Following the completion of the study, the participants are placed on appropriate recall schedule either at the Graduate Periodontics clinic or referred to their dentist of choosing.

Informed consent will be obtained from the patients. Appropriate steps will be taken to protect collected data and de-identify it before data analysis. Identifiers will be removed and the de-identified information may be used for future research without additional informed consent from the subjects. Patient information will be protected according to the privacy regulations of the federal Health Insurance Portability and Accountability Act of 1996 (HIPAA).

*\* Research specific procedure*

Planned Visits:

1. Pre-screening
  - a. Preliminary review of eligibility criteria\*
2. Screening
  - a. Confirm eligibility\*
  - a.b. Informed consent\*
  - c. Diagnostic casts
3. Fabrication of measurement stents
  - a. Fabrication of custom stent for measurement of alveolar ridge width\*
    - i. The stent will have positions for a Weiss modified curved bone caliper (Hu-Friedy®, Chicago, IL, USA) to be inserted at buccal and lingual, and measure ridge width at 2mm and 4mm apical to edentulous alveolar ridge.
  - b. Fabrication of custom stent for measurements on CBCT\*
    - i. Gutta-percha will be inserted into the holes created in the measurement stent to serve as a guide for the CBCT measurements. Patient will be wearing this stent when taking each CBCT.
  - c. Fabrication of custom radiographic stent\*
    - b.i. A custom bite registration will be attached to the sensor holder to take standardized bitewing radiographs, using the long-cone technique.
- 3.4. Pre-surgical data
  - a. Standardized CBCT
  - b. Standardized, periapical and bitewing radiograph
  - c. Non-standardized periapical radiograph
  - a.d.s. diagnostic casts, Intraoral photos
  - b.c. Surgical and restorative treatment planning
  - e. Fabrication of surgical guide

- ~~d. Fabrication of custom stent for measurement of alveolar ridge width\*~~
  - ~~i. The stent will have positions for a Weiss modified curved bone caliper (Hu-Friedy®, Chicago, IL, USA) to be inserted at buccal and lingual, at 2, 3, 4 mm apical to edentulous alveolar ridge.~~
  - ~~ii. Next to each of the 2, 3, 4mm insertion points, gutta-percha will be attached to serve as a guide for the CBCT measurements. Patient will be wearing this stent when taking each CBCT.~~
- ~~e. Fabrication of custom radiographic stent\*~~
  - ~~i. To take standardized periapical and bitewing radiographs, using the long-cone technique, a custom bite registration will be attached to the sensor holder.~~

#### 4.5. Surgical intervention

- a. Achieve appropriate anesthesia
- b. Reflect a full thickness flap
- c. Measure alveolar ridge width by using the custom stent and bone caliper\*
- d. Use the Densah® osseodensification drills (Versah®, LLC, Jackson, MI, USA), according to the manufacturer's recommendations, to create the appropriate osteotomy diameter for the planned implant size\*
- e. Measure alveolar ridge width by using the custom stent and bone caliper\*
- ~~e.f.~~ Take standardized ~~periapical and~~ bitewing and non-standardized periapical radiographs, ~~using the custom stent~~
- ~~f.g.~~ Place the appropriately sized implant (Roxolid® SLA® Bone Level Tapered; Straumann®, Institut Straumann AG, Basel, Switzerland)
- ~~g. Take standardized periapical and bitewing radiographs, using the custom stent~~
- h. Measure ISQ by using Osstell Beacon (Osstell®, Gothenburg, Sweden)
- i. Hand torque the appropriately sized cover screw or healing abutment
- j. Measure alveolar ridge width by using the custom stent and bone caliper\*
- k. Take standardized bitewing and non-standardized periapical radiographs
- ~~k.l.~~ Use xenograft if bone grafting at the time of implant placement is indicated
- ~~l.m.~~ Sutures the area
- ~~m.n.~~ Give Appropriate post-operative instructions
- ~~n.o.~~ Prescribe appropriate anti-inflammatory and antibiotics medications

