## 1. **Specific Aims**

Primary Aim:

Evaluate the efficacy of osseodensification technique in regards to increase in alveolar bone volume and density at time of implant placement and retention of this volume throughout osseointegration and loading.

Secondary Aim:

Evaluate the osseodensification technique for preparation of implant osteotomy, in regards to implant stability, survival and failure rate, probing pocket depth, plaque index, bleeding index, gingival index, interproximal crestal bone level changes, biological complications (i.e. peri-implant mucositis, peri-implantitis), and restorative complications (i.e. screw loosening, porcelain fracture). These outcomes will be evaluated from the time of implant placement until 1 year after final restoration is delivered.

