#### 7.8. 3-4-month follow-up after implant placement

- a. Evaluate wound closure, epithelialization, and any complications
- b. Evaluate pocket depth, plaque index, bleeding index, and gingival index
- c. Measure ISQ by using Osstell Beacon (Osstell®, Gothenburg, Sweden)
- d. Take standardized ~~periapical and~~ bitewing and non-standardized periapical

- radiographs
- e. Perform localized prophylaxis
- f. Take intraoral photos
- g. Uncover the implant, if needed (and 2-week follow-up after uncovering)
- ~~8.9.~~ Restoration by the restorative dentist
- ~~9.10.~~ 2-week follow-up after implant restoration
  - a. Evaluate pocket depth, plaque index, bleeding index, and gingival index
  - b. Evaluate biological (i.e. peri-implant mucositis, peri-implantitis) and restorative complications (i.e. screw loosening, porcelain fracture)
  - c. Take standardized ~~periapical and~~ bitewing and non-standardized periapical radiographs
  - d. Perform localized prophylaxis
  - e. Take intraoral photos
- ~~10.11.~~ 1-year Follow-up after implant restoration
  - a. Evaluate pocket depth, plaque index, bleeding index, and gingival index
  - b. Evaluate biological (i.e. peri-implant mucositis, peri-implantitis) and restorative complications (i.e. screw loosening, porcelain fracture)
  - c. Take standardized bitewing and non-standardized periapical radiographs
  - ~~e. Take standardized periapical and bitewing radiographs~~
  - d. Take standardized CBCT, limited to the implant site\*
  - e. Perform localized prophylaxis
  - f. Take intraoral photos
- ~~11.12.~~ Data analysis
  - a. Evaluation of change in peri-implant bone density, using the ImageJ software (National Institute of Health, Bethesda, Maryland, USA)\*
  - b. Statistical analysis of changes in the parameters throughout the study period\*

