#### 4. Inclusion / Exclusion Criteria

The inclusion criteria include:

1. Adult patients  $\geq 18$  years old
2. Able to understand and sign a written informed consent form and willing to fulfil all study requirements
3. Healed edentulous ridge that is planned for an implant restoration.
4. Experimental site has not been previously augmented with xenograft
5. Experimental site has at least 2 mm of cancellous bone

The exclusion criteria include:

1. Uncontrolled systemic disease
2. Currently smoking  $>10$  cigarettes/day
3. History of head/neck radiotherapy within the past five years
4. Current use of oral bisphosphonates or history of IV bisphosphonate use
5. Pregnant, expecting to become pregnant, or lactating women
6. Presence of active periodontal disease
7. Poor oral hygiene
8. Previous history of implant failure at the site

[figure not shown]
The early termination criteria include:

1. The researcher believes that it is not in the patient's best interest to stay in the study

2. Based on the exclusion criteria, the patient becomes ineligible to participate
3. Patient's medical condition requires interventions which preclude involvement in the study (radiation therapy, chemotherapy, etc)
4. Patient does not follow study related instructions
5. The study is suspended or canceled

If subjects do not qualify or decide not to be part of this study, same treatments can be performed but without being part of this study. If subjects decide not to receive the treatments, consequences and probable outcomes will be explained.

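### The post-implant caliper width (step j) is read after a cover screw or healing abutment is fitted (step i), so in healing-abutment sites the stent may not seat as it did at steps c and e

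*Combined protocol and SAP*

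**What the plan says.** All references are to the combined protocol and SAP.

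- **Three readings, same words.** In Section 3, Surgical intervention, steps c, e and j each read "Measure alveolar ridge width by using the custom stent and bone caliper". Step c comes before drilling, step e after drilling, and step j after the implant is in.
- **What comes between.** After step e the implant is placed (g), its stability quotient is measured (h), and then step i says "Hand torque the appropriately sized cover screw or healing abutment". Step j follows. No rule for choosing between the two components is given, and no height.
- **The stent.** Section 3 lists "Fabrication of custom stent for measurement of alveolar ridge width" at a visit before surgery. Its caliper positions are "to be inserted at buccal and lingual, and measure ridge width at 2mm and 4mm apical to edentulous alveolar ridge". What it rests on, whether it is open or relieved over the implant site, and how seating is checked are not described.
- **The site when the stent is made.** Section 4 requires a "Healed edentulous ridge that is planned for an implant restoration", so no component is present then.
- **One-stage sites are possible.** The 3-4-month visit makes uncovering conditional: "Uncover the implant, if needed (and 2-week follow-up after uncovering".
- **What the reading serves.** The primary aim (Section 1) covers "increase in alveolar bone volume and density at time of implant placement". Section 8 compares the state before expansion with later time points. It does not say whether step e or step j defines the immediate result.

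**The concern.** The stent is there to make the three readings comparable. Section 2 faults earlier studies for having no standardization, and this device is the plan's answer. As the steps are ordered, one of the three readings can be taken with something projecting from the implant that was absent at the other two, and only in some sites.

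Step j is also hard to replace. It is the only caliper reading with the implant in place, and no later visit lists another. Xenograft, where indicated, is added at step l, after j. The next listed source of post-implant width is the 2-week CBCT, which in a grafted site may include graft. Once the flap is sutured, the step j reading cannot be repeated. If the stent sits differently at step j, two quantities lose comparability in the affected sites: the total change from before drilling to after placement, and the part added by the implant itself.

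**Working it through.** The point rests on the order of steps, not on a planned figure. The only design figure, 90% power with about 40 implants (Section 8), plays no part in it.

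**Step 1. Conditions at each reading (Section 3, Surgical intervention).**

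| Reading | Drilled | Implant in | Component fitted |
|---|---|---|---|
| c | no | no | none |
| e | yes | no | none |
| j | yes | yes | cover screw or healing abutment |

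**Step 2. Which changes are exposed.**

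- e − c: neither reading has a component in place, so it is unaffected.
- j − c and j − e: both use step j, so both are exposed in healing-abutment sites.
- A cover screw would matter only if it stood high enough to touch the stent. The documents give no height.

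**Step 3. What a seating change would do.** Let W(z) be the ridge width at depth z below the crest. A stent that sits h mm too high reads W(z − h) instead of W(z). If width rises by s mm per mm of depth,

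error at an affected site ≈ −s × h,

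error in the mean ≈ −f × s × h, where f is the share of sites with a healing abutment.

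The documents give none of h, s or f. The values below are assumptions that show the range. The entries are absolute sizes in mm.

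| h (mm) | Per site, s = 0.25 / 0.5 / 1.0 | Mean with f = 0.5 |
|---|---|---|
| 0 (stent clears the component) | 0 / 0 / 0 | 0 / 0 / 0 |
| 0.5 | 0.125 / 0.25 / 0.5 | 0.0625 / 0.125 / 0.25 |
| 1 | 0.25 / 0.5 / 1.0 | 0.125 / 0.25 / 0.5 |
| 2 | 0.5 / 1.0 / 2.0 | 0.25 / 0.5 / 1.0 |

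Example: h = 1 and s = 0.5 give 1 × 0.5 = 0.5 mm at a site and 0.5 × 0.5 = 0.25 mm in the mean. At h = 2 the 2 mm position would read at the crest, because 2 − 2 = 0.

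**Step 4. Scale.** Section 2 cites mean expansions of 1.8 mm at the crest and 0.9 mm at the 10 mm mark from a retrospective study. A 0.5 mm shift would be 0.5 / 1.8 = 28% of the first. This gives an order of magnitude only, since this trial reads at 2 and 4 mm.

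**Step 5. Direction.** The error is an understatement only if s is positive, that is, if the ridge narrows toward the crest. If s is negative the sign reverses. The documents do not describe ridge shape after expansion.

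**The case against.** The strongest case on the other side is that the protocol never says the stent is closed over the implant site. A stent carried by neighbouring teeth, with clearance or an opening above the site, would seat identically at c, e and j, and h would be zero. A full-thickness flap is reflected at step b and closed only at step m, so no mucosa covers the crest at any of the three readings, and a lift cannot be taken from the height of an abutment above the gum. A stent that failed to seat would probably be noticed, and a hand-tightened component can be removed. Step e already measures expansion straight after drilling, which matches how the earlier studies measured it.

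Most of this stands. A reader might infer that the stent cannot seat and that the immediate-expansion result is therefore biased downward. The documents do not support that: support and relief are not described, the c-to-e change is untouched, and lift, slope and the share of one-stage sites are unknown. A reader might also infer that errors or missing values would follow bone quality or implant stability through the choice of component. No selection rule is given, so that is conjecture.

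What does not stand is the idea that flap reflection or tooth support settles the matter. A component tall enough to emerge through mucosa can still meet a stent formed over that mucosa, or one resting on the exposed bone. Only clearance over the site avoids contact, and none is specified. Relying on the operator to notice and remove the component leaves an unwritten step in a reading meant to be standardized.

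**Conclusion.** The point holds as a possibility, limited in scope. The only caliper reading with the implant in place is scheduled after a component is fitted, and the stent was made without that component and with no stated allowance for it. In healing-abutment sites, c-to-j and e-to-j may be read at a different level from the earlier readings, or be missing. The c-to-e change is sound.

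No size or direction can be derived from the documents. Over the assumed lifts of 0 to 2 mm and slopes of 0.25 to 1.0, the shift at an affected site runs from 0 to 2.0 mm, and zero is a real possibility. This is not evidence that the trial's result is biased. It is a small gap in standardization, worth closing because the reading cannot be repeated and the remedy costs almost nothing.

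**What to change.** Exchange steps i and j in the surgical list. Take the caliper reading after implant insertion and the stability measurement, with nothing projecting from the implant, and then fit the cover screw or healing abutment. Record which component was fitted at each site.

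This settles the caliper question whatever the stent design. It moves one measurement and does not touch which component a patient receives. The cost is two lines swapped and one field on the case report form, with no extra procedure, visit or staff.

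It would also help to state in Section 3 what the stent rests on and whether it is relieved over the site, because the stent is also worn at the later CBCTs, which the swap does not reach. Section 8 should name the reading, step e or step j, that defines immediate expansion.

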#### 5.6. 2-week follow-up after implant placement

- a. Evaluate wound closure, epithelialization, and any complications
- b. Take standardized CBCT, limited to the implant site\*
- c. Perform localized prophylaxis
- d. Take intraoral photos

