## 7. **Risks and Benefits**

In preparation of the dental implant osteotomy, the osseodensification technique uses non-subtracting drills to compress the trabecular bone to periphery of the osteotomy site rather than removing it. As a result, there will be more bone available at the site for primary stability of the implant. This technique also expands the alveolar ridge and allows for placement of wider implants without the additional need for bone augmentation. By avoiding bone augmentation, this technique will not only be more cost effective, but also reduces treatment time and morbidity.

Animal studies and human case reports have reported significant ridge expansion, but there is a lack of randomized controlled clinical trial in humans. Because of this gap in knowledge, we do not know if the implants prepared with osseodensification technique, using the Densah® burs by Versah®, will be successful in the long term and if the expanded bone is retained or resorbed. A retrospective studyxi observed 92.8% survival rate of the implants and high implant stability quotient value 6 weeks after placement. Details about marginal bone loss or status of peri-implant health or inflammation were not reported. Based on the

available data, the risk of implant failure is low when using the Densah® burs by Versah® to create the osteotomy and the risk of adverse events is similar to conventional techniques. We would like to further investigate if peri-implant health is maintained in long-term.

As with any surgery, there are risks involved, some common risks include, but are not limited to:

- Swelling and/or bruising and discomfort in the surgical area.
- Possible damage to adjacent teeth.
- Possible damage to nerves which causes numbness or altered feeling in the teeth. In rare cases the numbness is permanent.

Complications that do occur are often minor and can be treated. Every possible effort will be made to minimize the risks involved.

For volumetric assessment of the peri-implant bone, we propose to take a series of CBCT. The radiographs will be limited to the area of the implants to reduce the radiation exposure. Lead apron with thyroid collar will be used to limit radiation exposure to radiosensitive organs.

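### At sites given xenograft at surgery, CBCT gain and retention (and possibly late density) include graft, and Section 8 does not separate these implants

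*Combined protocol and SAP*

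**What the plan says.** The Surgical intervention visit in Section 3 lists its steps in order. Ridge width is measured by caliper before drilling (c), after drilling (e) and after implant placement: "j. Measure alveolar ridge width by using the custom stent and bone caliper". Bitewings are taken after drilling (f) and after placement: "k. Take standardized bitewing and non-standardized periapical radiographs". Step l then reads "Use xenograft if bone grafting at the time of implant placement is indicated", followed by suturing. No criterion, amount or location is given for the graft, and no record of its use is required.

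Section 3 summarises the imaging as "CBCT will be taken before and after osseodensification, and 1 year after delivery of final restoration". The visit list has no CBCT on the day of surgery, so the scan after osseodensification is the one at the 2-week visit ("Take standardized CBCT, limited to the implant site"). The last is at the 1-year visit ("d. Take standardized CBCT, limited to the implant site"). Bitewings are repeated at 3-4 months, 2 weeks after restoration and 1 year. No caliper reading is scheduled after surgery.

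The primary aim (Section 1) concerns the increase in bone volume and density at placement, and how much of the volume is kept through osseointegration and loading. Section 8 compares values before expansion with later time points and mentions a fixed-effects model for repeated measures. It does not mention grafting.

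**The concern.** Retention through loading is the gap that the Abstract and Section 2 give as the reason for the study. It rests on CBCT alone, because the caliper is used only at surgery. At a grafted site no CBCT falls between expansion and grafting, so no post-operative scan shows the expanded native ridge on its own. If the graft lies within the measured width, the ridge at 2 weeks and at 1 year is native bone plus graft, while the pre-operative scan is graft-free.

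The model does not remove this. Implant-level fixed effects absorb only what is constant over time. Graft enters after baseline, so its contribution goes into the time effect, and with no control arm nothing cancels it. What is at stake is whether a favourable 1-year CBCT result can be attributed to the drilling technique. If graft use is not recorded at surgery, it may not be reliably recoverable later.

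**Working it through.** **Sequence check.** Measurements set against step l:

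| Measurement | Time | Can include graft? |
|---|---|---|
| Caliper width c, e, j | surgery, before l | no |
| Bitewings f, k | surgery, before l | no |
| CBCT | pre-surgical | no |
| CBCT | 2 weeks; 1 year after restoration | yes |
| Bitewings (ImageJ density) | 3-4 months; 2 weeks and 1 year after restoration | yes, if graft lies in the measured region, which is not defined |

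**The plan's own figures.** The plan gives no figure for graft use, so there is nothing to reproduce on this point. The 90% power in Section 8 comes without an effect size, SD, alpha or test and cannot be re-derived; this point does not depend on it.

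**Inputs for an illustration.**
- Mean crestal expansion of 1.8 mm, from the retrospective study cited in Section 2. That study also gives 0.9 mm at the 10 mm mark. This trial measures at 2 and 4 mm, so both figures serve only for scale.
- Share of implants grafted, p: assumed 0.10 to 0.50.
- Width added at the measured level, g: assumed 0.5 to 1.5 mm, read as ridge and still present at 1 year.
- True native retention: assumed 50%, so 1.8 mm falls to 0.9 mm (half of 1.8, not the 10 mm figure).

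**Formulas.** Bias in mean CBCT gain = p × g. Apparent retention against the 2-week CBCT gain = (0.9 + pg)/(1.8 + pg). Apparent retention against a graft-free expansion = (0.9 + pg)/1.8.

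| p | g (mm) | Bias (mm) | vs 2-week CBCT | vs graft-free 1.8 mm |
|---|---|---|---|---|
| 0.10 | 0.5 | 0.05 | 0.95/1.85 = 51% | 0.95/1.80 = 53% |
| 0.25 | 1.0 | 0.25 | 1.15/2.05 = 56% | 1.15/1.80 = 64% |
| 0.50 | 1.5 | 0.75 | 1.65/2.55 = 65% | 1.65/1.80 = 92% |

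The denominator matters, and Section 8 does not say which one applies.

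**Two limits on direction.**
- If graft persists, the absolute loss from 2 weeks to 1 year is (1.8 + pg) − (0.9 + pg) = 0.9 mm, which is correct. Only gain from baseline and percentage retention are biased.
- If graft were wholly lost by 1 year, retention against the 2-week CBCT would instead be understated, at 0.9/1.85 = 49% to 0.9/2.55 = 35%, while the 2-week gain would still be overstated.

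**The case against.** The case on the other side has several parts.

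- **Much of the primary aim is clean.** A reader might infer that the whole aim, gain as well as retention, is confounded. It is not. Section 1 places the gain at implant placement, and that is measured before any graft by the caliper (c, e, j) and by the pre-surgical, f and k bitewings. This stands.
- **Eligibility is consistent.** A reader might see a contradiction between step l and the inclusion criterion "Experimental site has not been previously augmented with xenograft". Section 2 reports the manufacturer's advice not to densify xenograft. That concerns what is drilled, and step l comes after drilling, so the two are compatible. This stands.
- **Silence is not a rule.** Section 8 does not state that grafted and ungrafted implants are pooled, and the plan does not say how CBCT or ImageJ readers treat graft. Nor does it say that grafts go where expansion fell short; it says only that they are used if indicated. Non-random grafting is plausible but is an inference. This too stands. Even so, following Section 8 as written gives one comparison over time with no separation by graft.
- **Need for a graft is not a stated outcome.** Section 7 says the technique "allows for placement of wider implants without the additional need for bone augmentation", but as a general benefit, not a hypothesis. That is correct. The proportion grafted is still needed to interpret results by graft status.
- **Restricting to ungrafted implants brings its own bias.** Graft status arises after treatment, and ungrafted sites may be those that did well. This is a sound objection to making them the sole primary set, and the fix allows for it.
- **The study is a mainly descriptive case series, and the grafted share could be near zero.** Both points are fair and limit the severity.

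**Conclusion.** The point holds in a limited form. The order of steps and the lack of any graft record or stratum are plain in the documents. At grafted sites, CBCT gain from baseline, percentage retention and possibly late density are open to bias, in the technique's favour while graft persists. Ungrafted sites, immediate caliper expansion and immediate density change are not affected.

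The size cannot be determined. The 0.05 to 0.75 mm overstatement of mean gain, and the apparent retention of 51 to 65% or 53 to 92% in place of 50%, rest on assumed graft shares and thicknesses, on graft lying within the measured width and being read as ridge, and on its persisting to 1 year. Confidence is high on the sequence and low on the impact. This should be fixed, but it does not invalidate the study. Whether grafting should be allowed is a clinical matter and is not judged here.

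**What to change.** Leave surgical care as it is and change only recording and analysis.

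1. Add to the case report form, per implant, whether xenograft was placed at step l and on which surface.
2. In Section 8, estimate immediate expansion from the pre-graft caliper widths in all implants.
3. Report CBCT gain and retention, and post-surgical density, separately for ungrafted and grafted implants, or fit a graft-by-time term. Name the retention denominator. Attribute retention to osseodensification only from the ungrafted stratum, and state that this stratum is selected after treatment.
4. Report the proportion grafted with a 95% CI beside those results, so that the selection is visible.

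The cost is one form entry, some wording in Section 8 and a less precise retention estimate. With about 40 implants, 10 to 50% grafted leaves 36 to 20 ungrafted. If the SD is unchanged and implants are independent, the standard error rises by a factor of √(40/36) = 1.05 to √(40/20) = 1.41.
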